5.2.2 DEVICE SUCCESS ENDPOINT

Device Success will be assessed at 1 month, 6 months and annually and is defined as:

- Alive, with
- Original intended device in place, and
- No additional surgical or interventional procedures related to the device, and

- TR reduction (assessment made by change in EROA) compared to baseline and TV gradient ≤ 5 mmHg

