13.3 ANALYSIS POPULATION

The analysis population will be grouped into four analysis cohorts that in total comprise all subjects enrolled in this study. The analysis cohorts are defined below:

- Enrolled Cohort: all subjects enrolled in the study
- As Treated (AT) Cohort: all subjects who are enrolled and undergo the study procedure (chest incision)
- Implanted Cohort: all subjects who undergo the study procedure (chest incision), receive and retain the investigational device upon leaving the procedure room
- Roll-In Cohort: first subject enrolled and treated at a center that does not have previous device or procedure experience and is classified as a “roll-in” subject

The primary endpoint will be reported based on the AT cohort. For the secondary endpoints and clinical outcomes, technical success analysis will be performed for the AT cohort, while device success, procedure success and clinical outcomes analyses will be performed for the implanted cohort. Roll-In subjects will be analyzed separately. Subject listings for adverse events, deaths will include all enrolled subjects.

For subjects with major protocol violations, which include but are not limited to study criteria and informed consent violations, a secondary analysis will be conducted in which those subjects will be excluded from the implanted cohort analyses.

Further analysis plans will be outlined in the statistical analysis plan.

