13.5 ADDITIONAL ENDPOINT ANALYSIS

All statistical analyses will be performed by Edwards Lifesciences. Subject data listings and tabular presentations of results will be provided. All clinically relevant baseline and follow-up variables will be tabulated. Descriptive statistics will be used for continuous variables (e.g., mean, standard deviation, sample size, minimum, and maximum) and frequency tables or proportions for discrete variables.

Kaplan Meier estimates will be performed at the pre-specified follow-up times to project the estimates for time-related safety endpoints. The rate of freedom from all-cause mortality at 6 month, 1 year, 2 years, and 3 years will be estimated in addition to the primary endpoint which is established at 30 days post procedure.

Echocardiographic data will be analyzed by a core laboratory. The improvement from baseline items will be presented as shift from baseline for each of the pre-specified follow-up periods. Subjects that are missing a baseline or follow-up values will be excluded from the analysis.

Subjects that undergo any type of repair or replacement procedure for the tricuspid valve will be excluded from the implant cohort analyses at the time of the re-intervention.

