Device Detachment	Separation, under the action of applied stress or strain, of any part of the investigational device that was previously intact.
Device Embolization	Refer to ISO 5840-3 definition
Device Malfunction	Refer to ISO 14155 definition
Device Migration	Refer to ISO 5840-3 definition
Device Success	
Device Success (at 1 month, 6-months and annually):
 
 • Alive, with • Original intended device in place, and • No additional surgical or interventional procedures related to the device, and • TR reduction (assessment made by change in EROA) compared to baseline and TV gradient $\leq 5\text{mmHg}$
Embolism	
Free flowing blood clot or lesion material that is located in the systemic or pulmonary circulation.
 
A peripheral embolic event is an operative, autopsy or clinically documented embolus that produces symptoms from complete or partial obstruction or a peripheral (noncerebral) artery.

Emergency Surgery
	
Emergent Salvage: The patient is undergoing CPR en route to the operating room or prior to anesthesia induction
 
Emergent: All of the following conditions are met:
 
 • Not elective status • Not emergent salvage status • Procedure required before procedure room exit in order to minimize chance of further clinical deterioration • Any surgical procedure on the previously implanted study device (repair, alteration or replacement) or study procedure access site post-implant procedure 
Elective: The patient’s cardiac function has been stable in the days or weeks prior to the operation. The procedure can be deferred without increased risk of compromised cardiac outcome.

Endocarditis
	
An inflammation of the inside lining of the heart chambers and heart valves (endocardium). Endocarditis can involve the heart muscle, heart valves, or lining of the heart.

Enrollment
	
Subject enrollment in this clinical study is established when a subject has signed the informed consent form agreeing to participate in the study and has been deemed eligible for study participation by meeting the study criteria.

Explant
	
Removal of the study device after completion of the implant procedure for any reason.

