New York Heart Association Classification (NYHA Class)	
Class I: Patients with cardiac disease but without resulting limitations of physical activity.
 
Class II: Patients with cardiac disease resulting in slight limitation of physical activity. Patients are comfortable at rest. Ordinary physical activity results in fatigue, palpitation, dyspnea, or anginal pain.
 
Class III: Patients with cardiac disease resulting in marked limitation of physical activity. They are comfortable at rest. Less than ordinary physical activity causes fatigue, palpitation dyspnea, or anginal pain.
 
Class IV: Patients with cardiac disease resulting in inability to carry on any physical activity without discomfort. Symptoms of cardiac insufficiency or of the anginal syndrome may be present even at rest. If any physical activity is undertaken, discomfort is increased.

Nonstructural Dysfunction	Abnormality extrinsic to the repair device that results in valve dysfunction (stenosis, regurgitation or both)
Patient	A person with the disease (tricuspid regurgitation) being screened to participate in the clinical study.

Peripheral Thromboembolic Event	See “Embolism”
Pre-Existing Condition	A pre-existing condition is one that is present at the start of study treatment.
Primary Endpoint	The primary endpoint for the study will assess the all-cause mortality of the as treated cohort at 30 days compared to a literature derived Performance Goal based on high-risk surgical outcomes for tricuspid repair/replacement.
Procedural Success	Procedural Success (at 1 month): 
 • Device Success, and • None of the following device or procedure related SAEs: 
 • Life threatening bleeding • Major vascular or cardiac structural complications requiring intervention • Pericardial effusion requiring drainage or surgery (includes tamponade) • Stage 2 or 3 acute kidney injury (includes new dialysis). • Severe heart failure or hypotension requiring IV inotrope, ultrafiltration or mechanical circulatory support • Prolonged intubation > 48 hours
Prosthesis	An artificial substitute
QoL	Quality of Life
Reintervention	Any intervention on the previously implanted study device (repair, alteration or replacement) or study procedure access site post-implant procedure.
Renal Failure	See “Acute Kidney Injury (AKI)”

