2.4 Analysis Populations

The analysis population will be grouped into four analysis cohorts that in total comprise all subjects enrolled in this study. The analysis cohorts are defined below:

- Enrolled Cohort: all subjects enrolled in the study
- As Treated (AT) Cohort: all subjects who are enrolled and undergo the study procedure (chest incision)
- Implanted Cohort: all subjects who undergo the study procedure (chest incision), receive and retain the investigational device upon leaving the procedure room
- Roll-In Cohort: first subject enrolled and treated at a center that does not have previous device or procedure experience and is classified as a “roll-in” subject

The primary endpoint will be reported based on the AT cohort. For the secondary endpoints and clinical outcomes, technical success analysis will be performed for the AT cohort, while device success, procedure success and clinical outcomes analyses will be performed for the implanted cohort. Roll-In subjects will be analyzed separately. Subject listings for adverse events, deaths will include all enrolled subjects.

For subjects with major protocol violations, which include but are not limited to study criteria and informed consent violations, a secondary analysis will be conducted in which those subjects will be excluded from the implanted cohort analyses.

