3.3 Additional Endpoint Analysis

Kaplan Meier estimates will be performed at the pre-specified follow-up times to project the estimates for time-related safety endpoints. The rate of freedom from all-cause mortality at 6 month, 1 year, 2 years, and 3 years will be estimated in addition to the primary endpoint which is established at 30 days post procedure.

Echocardiographic data will be analyzed by a core laboratory. The improvement from baseline for selected items will be presented as shift from baseline for each of the pre-specified follow-up periods. Subjects that are missing a baseline or follow-up values will be excluded from the analysis.

Subjects that undergo any type of repair or replacement procedure for the tricuspid valve will be excluded from the implant cohort analyses at the time of the re-intervention.

The average overall (general) quality of life at baseline, 1 month, 6 months and annually for 3 years and the changes from baseline to follow up will be summarized by mean and standard deviation for the implanted cohort. Patients that are missing a baseline or follow up values will be excluded from the analysis.

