4.3 Additional Endpoint Analysis

The following secondary endpoints and clinical outcomes will also be assessed

4.3.1 Technical Success (at exit from procedure room):

- Alive, with

- Successful access, delivery and removal of the delivery systems, and
- Deployment and correct positioning of the intended device, and
- No need for additional emergency surgery or re-intervention related to the device or access procedure

4.3.2 Device Success (at 1 month, 6 months & annually):

- Alive, with
- Original intended device in place, and
- No additional surgical or interventional procedures related to the device, and
- TR reduction (assessment made by change in EROA) compared to baseline and TV gradient $\leq 5\text{mmHg}$

4.3.3 Procedural Success (at 1 month):

- Device Success, and
- None of the following device or procedure related SAEs:
 - Life threatening bleeding
 - Major vascular or cardiac structural complications requiring intervention
 - Pericardial effusion requiring drainage or surgery (includes tamponade)
 - Stage 2 or 3 acute kidney injury (includes new dialysis).
 - Severe heart failure or hypotension requiring IV inotrope, ultrafiltration or mechanical circulatory support
 - Prolonged intubation > 48 hours

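### The rule that drops subjects from implanted-cohort analyses after a tricuspid repair or replacement names no endpoint, so as written it removes defined Device Success failures from the denominator

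*SAP*

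**What the plan says.** SAP 3.3 provides that subjects with any kind of "repair or replacement procedure for the tricuspid valve will be excluded from the implant cohort analyses at the time of the re-intervention". Protocol 13.5 has the same rule, opening with "Subjects that undergo any type of repair or replacement procedure for the tricuspid valve". Neither section names the endpoints it covers.

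SAP 2.4, matching protocol 13.3, assigns the endpoints: "device success, procedure success and clinical outcomes analyses will be performed for the implanted cohort". Device Success is assessed at 1 month, 6 months and yearly to 3 years. Its components include "Original intended device in place, and" (SAP 4.3.2) and "No additional surgical or interventional procedures related to the device, and" (protocol 5.2.2). Procedural Success at 1 month requires Device Success.

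Two other rules bear on the same subjects. SAP 3.5 and protocol 13.6 use available data only, without imputation. Under protocol 8.10, a subject whose device is explanted is followed for safety only and leaves the study at the 6 month visit.

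**The concern.** One event has two consequences that cannot both apply. The endpoint definition makes a device-related tricuspid procedure a failure, and the exclusion rule takes the same subject out of the analysis in which that failure would count. No section says that such a subject stays in as a failure.

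Device performance is one of the two stated study objectives, and protocol 2 says the data will support regulatory approval. If failures are removed as they occur, the reported Device Success rate rises because subjects needed another procedure.

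**Working it through.** **1. The sections applied to one subject.** Take a device-related tricuspid repair at month 4.

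| Visit | Endpoint definition | Excluded from the procedure onward | Event counted, later data dropped |
|---|---|---|---|
| 1 month | assessed on components | same | same |
| 6 months | failure | not in denominator | failure |
| 1, 2, 3 years | failure | not in denominator | not in denominator |

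The last column is the more lenient reading of the exclusion. It keeps the failure once and then loses it. The last row of the second column takes the no-further-procedure component as cumulative, since it carries no time limit.

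**2. Who is covered.** The rule does not reach deaths, or failures on EROA or gradient. Nor does it clearly reach an explant, defined in protocol 19 as "Removal of the study device after completion of the implant procedure for any reason", when no valve repair or replacement is done. It does reach a subject with an unrelated tricuspid procedure and the device still in place, who is not an automatic failure.

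**3. Inputs.** The plan gives no Device Success or re-intervention figure to reproduce. N = 63 is the planned analysable number in protocol 13.1. It reproduces with a one-sided exact binomial test of 18% against 7.5%: rejecting at 6 or fewer deaths has size 0.0487 and power 0.808. That figure is not disputed. It is used here only as an assumed implanted number, which could differ because the implanted cohort is a subset of the treated one. The successes x and the excluded subjects R are assumptions.

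**4. If all R excluded subjects are failures.** The rate by definition is x/N and the reported rate is x/(N−R), so the rate is multiplied by N/(N−R). For R = 3 that is 63/60 = 1.050; for R = 6 it is 63/57 = 1.105. Intervals are Clopper-Pearson 95%, as in SAP 3.1. Shifts are taken from unrounded fractions.

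| x | R | Reported rate | 95% CI | Shift (points) |
|---|---|---|---|---|
| 38 | 0 | 38/63 = 60.3% | 47.2–72.4 | – |
| 38 | 1 | 38/62 = 61.3% | 48.1–73.4 | +1.0 |
| 38 | 3 | 38/60 = 63.3% | 49.9–75.4 | +3.0 |
| 38 | 6 | 38/57 = 66.7% | 52.9–78.6 | +6.3 |
| 32 | 6 | 32/57 = 56.1%, from 32/63 = 50.8% | not computed | +5.3 |
| 44 | 6 | 44/57 = 77.2%, from 44/63 = 69.8% | not computed | +7.4 |

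**5. If some excluded subjects would have been successes.** With u such subjects the reported rate is (x−u)/(N−R). This exceeds x/N only if u/R < x/N. For x = 38 and R = 3, u = 1 gives 37/60 = 61.7% and u = 2 gives 36/60 = 60.0%, slightly below 60.3%.

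**6. What else removes these subjects.** A subject explanted before the 6 month visit has safety follow-up only and then exits. With no later echo or visit data, the available-data rule can drop that subject at 1, 2 and 3 years even if the SAP 3.3 sentence were deleted.

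**The case against.** The strongest reply is that the sentence sits between the echo-shift and quality-of-life paragraphs and was meant for those measures. That may be the intent. But it stands as its own paragraph and refers to the implanted-cohort analyses without qualification, so a programmer has no basis for confining it.

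A second reply is that protocol 8.10 and the available-data rule already remove explanted subjects. This stands. It limits what can be attributed to SAP 3.3, and it means that amending SAP 3.3 and protocol 13.5 alone would not be enough.

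A third is that excluding poor responders could also flatter the change-from-baseline summaries. That is a fair caution about reading them. However, those summaries have no predefined failure category, so exclusion there does not contradict an endpoint definition as it does for Device Success.

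Finally, the consequences are bounded. Device Success is descriptive and has no performance goal. Re-interventions reported as adverse events stay visible: "Subject listings for adverse events, deaths will include all enrolled subjects". Listings do not, however, correct a reported percentage.

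A reader might infer that the re-intervention rate is undercounted too. That holds only if the triggering event is itself excluded; under the censoring reading it is counted.

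**Conclusion.** The point holds and should be fixed, as an unrestricted exclusion that conflicts with the definition of Device Success and, for events up to 1 month, Procedural Success. The missing endpoint limit is plain on the text under either reading of the timing.

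The size is illustrative. With 63 implanted and all excluded subjects failures, 3 exclusions move 60.3% to 63.3%. Six exclusions add about 5 to 7 points across starting rates of 50.8% to 69.8%. For small R the shift is well inside an interval about 25 points wide.

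Three stronger readings are not supported:
- That Device Success will certainly be inflated. The shift is upward only if excluded subjects succeed less often than the rest, and the documents give no counts.
- That the whole loss of failures at the annual visits comes from this sentence. Protocol 8.10 and the available-data rule can remove some of the same subjects.
- That the trial's main conclusion is at risk. The 30-day mortality test uses the As Treated cohort, which the rule does not touch.

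**What to change.** - In SAP 3.3 and protocol 13.5, limit the exclusion to change-from-baseline summaries (EROA, NYHA class, walk distance, SF-12, KCCQ, weight).
- For Device and Procedural Success, keep re-intervened implanted subjects in the denominator and apply the components already written. Assess a subject with an unrelated tricuspid procedure and the device in place on those same components.
- In SAP 3.5 and protocol 13.6, state that a known failure component (death, original device no longer in place, or a device-related procedure) is sufficient data. The subject then counts as a failure at that and every later visit, without echo data and after study exit under protocol 8.10. This uses an observed outcome and is not imputation.
- State that the re-intervention that triggers the exclusion is counted in the re-intervention rate.

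The cost is a SAP revision and a written protocol amendment under protocol 17.6. No new data are needed. Reported Device Success may be less favourable.

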3.5 Missing Data Handling

All statistical analysis on the endpoints will be performed using only those patients with available data required for endpoint analysis. No missing value imputation will be performed.

No imputation will be done if the date variables are completely missing. For partial dates, only adverse event (AE) onset date will be imputed as follows:

- 1) If both month and day are missing
 - a. If the AE onset year is the same year as index procedure then use index procedure date to impute this AE onset date
 - b. Otherwise, assign January 1st for this AE onset date
- 2) If only day is missing
 - a. If the AE onset year and month are the same as the procedure ones then use the index procedure date to impute the AE onset date
 - b. Otherwise, assign '01' as the day for the AE onset date

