4.3.4 Clinical Outcomes (at 1 month, 6 months & annually)

- Re-hospitalization rates for the underlying condition (heart failure)
- Re-intervention rates for the underlying condition (tricuspid regurgitation) Change in Tricuspid Regurgitation (assessment made by change in EROA) from baseline
- Change in peripheral edema as assessed by subject weight loss (kilograms) from baseline
- Change in NYHA Class from baseline
- Change in 6 minute walk test distance (meters) from baseline
- Change in Quality of Life as assessed by the SF-12 and KCCQ questionnaires from baseline

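### NYHA, six-minute walk and quality-of-life changes are summarised only in subjects who have a value at the visit, so they are likely to overstate benefit in the implanted cohort, increasingly at later visits.

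*SAP*

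**What the plan says.** The general rule is in SAP 3.5: "All statistical analysis on the endpoints will be performed using only those patients with available data required for endpoint analysis". It continues: "No missing value imputation will be performed". Protocol 13.6 says the same. This rule is the one that reaches NYHA class and six-minute walk distance.

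SAP 3.3 repeats it at the end of the quality-of-life paragraph: "Patients that are missing a baseline or follow up values will be excluded from the analysis". That sentence covers quality of life only. The similar sentence in Protocol 13.5, "Subjects that are missing a baseline or follow-up values will be excluded from the analysis", follows the text on core-laboratory echocardiography.

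SAP 4.3.4 lists the outcomes at 1 month, 6 months and annually: "Change in NYHA Class from baseline", "Change in 6 minute walk test distance (meters) from baseline" and "Change in Quality of Life as assessed by the SF-12 and KCCQ questionnaires from baseline". SAP 2.4 fixes the cohort: "device success, procedure success and clinical outcomes analyses will be performed for the implanted cohort".

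Two further rules remove subjects. SAP 3.3 and Protocol 13.5 take anyone with a later tricuspid repair or replacement out of the implanted-cohort analyses from that time. Under Protocol 8.10, an explanted subject has safety evaluations only and leaves the study at 6 months.

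Neither document says how death, or being too ill to walk or to answer a questionnaire, enters a change score. No sensitivity analysis for missing data is planned. The one secondary analysis (SAP 2.4) leaves out major protocol violators, so it removes more subjects.

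**The concern.** Subjects can lack a later value because they died, became too ill to attend, had the device removed or needed another tricuspid procedure. These are reasons to expect that they did worse than those who were measured. The paired change then describes a selected group, and in a high-risk cohort followed for 3 years that group shrinks with time.

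The study has no control arm against which the selection could be judged. Protocol section 2 says that the data will be used to seek regulatory approval, and Protocol 3.3 says that clinical benefit is not yet known. NYHA class, walk distance, KCCQ and SF-12 are the outcomes that describe how subjects feel and function. A reader could take a favourable paired mean at 3 years as the result for everyone who received the device.

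**Working it through.** **The plan's own figure.** The documents give none for these outcomes. The only sample-size figure is for 30-day mortality: 63 subjects for at least 80% power (7.5% against 18%). An exact one-sided binomial test with 63 subjects rejects at 6 deaths or fewer, with alpha 0.0487 and power 0.808. The figure reproduces and this point does not affect it.

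**Who contributes to a paired change at 3 years**
- Dead: no value.
- Withdrawn, lost or not attending: no value and no imputation (SAP 3.5).
- Explanted: safety evaluations only, then exit at 6 months (Protocol 8.10).
- Tricuspid re-intervention: removed from that time (SAP 3.3).
- Alive, attending, device retained, no re-intervention: included.

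**Effect on a mean.** Let m be the share without a value. The paired mean exceeds the all-subject mean by m x (mean change in those measured - mean change in those not measured). Assume a mean of +15 points in those measured. The other inputs are also assumptions.

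| m | unmeasured change +15 | unmeasured change 0 | unmeasured change -10 |
|---|---|---|---|
| 10% | 0 | 1.5 | 2.5 |
| 30% | 0 | 4.5 | 7.5 |
| 50% | 0 | 7.5 | 12.5 |

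The excess is zero only if those without a value would have changed as much as those measured. A dead subject has no change score, so for deaths this shows only the effect of assigning one.

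**Effect on a proportion.** Assume that 60% of assessed subjects improve, that 10% of survivors have no visit and that annual mortality is constant. S is survival to the visit.
- Upper figure, missing survivors improve at the same rate as those assessed: S x 0.60.
- Lower figure, missing survivors not improved: S x 0.90 x 0.60.

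| Annual mortality | S, 1 year | Alive and improved, 1 year | S, 3 years | Alive and improved, 3 years |
|---|---|---|---|---|
| 5% | 0.950 | 51.3-57.0% | 0.95³ = 0.857 | 46.3-51.4% |
| 15% | 0.850 | 45.9-51.0% | 0.85³ = 0.614 | 33.2-36.8% |
| 25% | 0.750 | 40.5-45.0% | 0.75³ = 0.422 | 22.8-25.3% |

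Leaving missing survivors out of the denominator gives S x 0.90 x 0.60 / (1 - 0.10 x S). At 3 years that is 50.6%, 35.3% and 23.8%, inside each range. In every row the proportion among assessed subjects stays at 60% at both visits.

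**The case against.** **Deaths are not lost from the report.** A reader might infer that they are. The documents do not support this. Kaplan-Meier survival is estimated at 6 months and at 1, 2 and 3 years, death listings cover all enrolled subjects, and Device Success requires the subject to be alive. Protocol 13.5 lists sample size among the descriptive statistics, so a falling number would be visible. This stands. However, none of these joins survival to function or says why the number fell. Device Success is also analysed in the implanted cohort, so the re-intervention exclusion, read literally, reaches it too.

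**These are not the study's formal evidence.** It is a safety study with one hypothesis, on 30-day mortality, and the functional outcomes are descriptive. This stands, and it keeps the point small.

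**The illustration compares two different quantities.** This also stands. The plan specifies no proportion improved, so the 60% is an assumption and not a planned result. At 15% annual mortality, the step from 60% to 36.8% at 3 years is due to survival alone and would appear even if the paired summary were exactly right for survivors. Only the step from 36.8% to 33.2% comes from missing survivors. The table therefore shows how far the two descriptions of the cohort can part, and does not measure a bias.

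**Overstatement is not proven.** A reader might go further and infer that improvement is certainly overstated, or that most implanted subjects could be dead or worse. The documents show neither. The direction depends on sicker subjects being the ones missing. Not improved includes unchanged: at 15% mortality, 38.6% would be dead at 3 years and 24.6% alive but not improved (0.614 x 0.40).

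**Conclusion.** The point holds as a reporting weakness. By rule, changes in NYHA class, walk distance, KCCQ and SF-12 describe attending survivors who kept the device and had no re-intervention. They are likely to overstate benefit in the implanted cohort, and more so as follow-up lengthens. This rests on the judgement that subjects without a value fared worse on average, which is plausible here but not shown.

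The documents give nothing from which to fix the size. Under the stated assumptions, alive and improved at 3 years is 46-51%, 33-37% or 23-25% of all implanted subjects at 5%, 15% or 25% annual mortality, beside 60% among those assessed. The primary endpoint, its test and its sample size are unaffected.

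**What to change.** In SAP 3.3 and 3.5, keep the paired summary as descriptive and add the following at each visit:

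- The proportion alive and improved for NYHA class, KCCQ and six-minute walk, with the Clopper-Pearson intervals that SAP 3.1 already provides.
- As denominator, all implanted subjects who have reached or would have reached the visit, including those explanted or re-intervened.
- Death, explant and tricuspid re-intervention counted as not improved.
- Living subjects without a value shown both ways: as not improved, and left out. Treat withdrawn and lost subjects not known to have died in the same way.
- A definition of improved for each outcome, fixed before analysis: for example at least one NYHA class, and a stated threshold for KCCQ and for walk distance.
- Beside each paired mean, the numbers implanted, dead, withdrawn, explanted or re-intervened, missing and paired.

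The cost is one extra table per outcome, from data already collected and with no modelling. The downside for the sponsor is less favourable figures. This is a cheap improvement and not a condition for the study's main conclusion.
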